8.3.7. Laboratory Tests: Hematology, Biochemistry, Urinalysis, Pregnancy Tests

Laboratory assessments and pregnancy test should be performed by a central laboratory designated by the Sponsor and/or by a local laboratory, according to instructions in Table 8-2 below.

These laboratory assessments are to be performed according to the schedule presented in Table 1-1 and Table 1-2

On C1D1, hematologic, renal and hepatic laboratory assessments required for inclusion (see criteria 9 -Section 5), and for defining suitability for cisplatin administration (see Table 8-2 and Section 6.1.2.2) should be assessed by a central laboratory. If the previous central laboratory results are older than 7 days, the hematologic, renal and hepatic laboratory assessments should be rechecked by a local laboratory before the first dose administration.

On C1D1, negative serum pregnancy status should also be rechecked locally by serum or urine test only if the previous central laboratory result is older than 7 days.

On C2D1 and C3D1, suitability for chemotherapy administration (see Table 8-2 and Section 6.1.2.2) should be evaluated based on local laboratory values irrespectively of the samples sent to the central laboratory.

Renal function must be monitored 48 hours (±12 hours) after cisplatin infusion (i.e C1D4, C2D4, C3D4) based on local laboratory values of creatinine, eGFR, sodium, potassium, calcium, and magnesium.

The initial pregnancy test should be performed on serum during screening period by a central laboratory (Table 8-2 and Section 8.1.3). Subsequent pregnancy tests will be performed locally using urine or serum according to the schedule in Table 1-1 and Table 1-2, or if clinically indicated.

Table 8-2 Assessments to be performed by a central laboratory or by a local laboratory according to study visit

Visit	Central laboratory designated by the Sponsor	Local laboratory
During screening	HBV/HCV/HIV tests if no local results obtained within 2 weeks before ICF signature	Local results within 2 weeks before ICF signature accepted for HBV/HCV/HIV tests
	 HPV status by p16 IHC if no available report and test not available locally 	HPV status by p16 IHC if no available report
	o Blood hematology (Table 8-3)	
	o Blood biochemistry (Table 8-3)	
	Serum pregnancy test	
	o Urinalysis (Table 8-3)	

Visit	Central laboratory designated by the Sponsor	Local laboratory
C1D1	All hematology and biochemistry assessments (full panel) mentioned in Table 8-3.	The following assessments should be performed locally if the previous central laboratory results are older than 7 days: Laboratory assessments specified in inclusion criteria 9 and assessments required to evaluate suitability for cisplatin: eGFR, ANC, platelet counts, hemoglobin, AST, ALT, total bilirubin Serum or urine pregnancy test If central laboratory assessments for eGFR, ANC, platelet counts, hemoglobin, AST, ALT and total bilirubin were performed within 7 days before C1D1, they should not be repeated locally on C1D1.
C2D1 and C3D1 All visits after randomization, except	 All hematology and biochemistry assessments (full panel) mentioned in Table 8-3. Coagulogram (Table 8-3) Urinalysis (Table 8-3) Hematology, coagulogram, blood chemistry and urinalysis assessments (Table 8-3), to be 	Laboratory assessments required to evaluate suitability for chemotherapy administration: eGFR, platelet counts, ANC, hemoglobin rate Serum or urine pregnancy test Serum or urine pregnancy test
C1D1; C2D1 and C3D1	performed according to schedule presented in Table 1-1 and Table 1-2	
Renal function monitoring 48 hours (±12 hours) after cisplatin infusion (C1D4, C2D4, C3D4)	n.a.	Creatinine, eGFR Sodium, potassium, calcium magnesium

Abbreviations: ALT: alanine aminotransferase; ANC: absolute neutrophil count; AST: aspartate aminotransferase; CxDx: cycle x Day x; eGFR: estimated glomerular filtration rate; HBV: Hepatitis B virus; HCV: Hepatitis C virus; HIV: Human immunodeficiency virus; HPV: human papillomavirus; ICF: informed consent form; IHC: immunohistochemistry; n.a.: not applicable.

Blood samples for hematology, biochemistry and coagulogram assessments should be taken before treatment administration., Blood sample for coagulogram should be collected (see schedule of relevant visits in Table 1-1).

Details on all laboratory procedures, collections, shipment of samples and reporting of results, alerting of extreme values and notable values by the central laboratory are provided to Investigators in the laboratory manual of extreme values.

The Investigator is responsible for reviewing all laboratory reports for participants during the study and evaluating any abnormalities for clinical significance.

If a local laboratory is used, the local laboratory values will have to be recorded on the Local Laboratory Results eCRF if clinically significant.

Furthermore, local laboratory assessments may also be performed according to medical needs (e.g., during medical emergencies, or for treatment-related decisions, etc.) when the Investigator needs quick results to make treatment decisions.

Clinically significant laboratory abnormalities occurring since the ICF signature are to be recorded in the eCRF as AEs.

Further details on sample collection, handling and shipment will be provided in the laboratory manual.

Table 8-3 Assessments to be performed by a central laboratory designated by the Sponsor

Virology	HBV: HBV sAg and Anti-HepB core IgG HCV: HCV-antibody and HCV-RNA by PCR HIV1/2		
Hematology	White blood cell count (total and differential) Red Blood cell count, Hemoglobin Platelet count ANC		
Coagulogram	Prothrombin Time or INR, if applicable (e.g., under oral anticoagulation medication) Activated partial thromboplastin time Fibrinogen		
Blood Biochemistry (full panel)	Creatinine and eGFRa Lipase Total protein Albumin Potassium Total bilirubin (If >ULN: direct bilirubin should also be measured) ALP AST ALT C-reactive protein Amylase Lipase Sodium Potassium Calcium Magnesium Urea Uric acid		
Blood Biochemistry (minimum panel)	Creatinine Total bilirubin (If >ULN: direct bilirubin should also be measured) ALT AST ALP		
Urinalysis	Dipstick test for: Red blood cells Protein Glucose Leucocytes Ketones		
Pregnancy test	Serum pregnancy test (β-HCG) during screening in women of childbearing potential, local serum or urine tests thereafter.		

Abbreviations: ALP: alkaline phosphatase; **ALT:** alanine aminotransferase; **ANC:** absolute neutrophil count; **AST:** aspartate aminotransferase; β -HCG: Human chorionic gonadotropin; eGFR: estimated glomerular filtration rate; HBV: hepatitis B virus; HCV: hepatitis C virus; HIV: human immunodeficiency virus; INR: International normalized ratio; sAg: surface antigen; ULN: upper limit of normal.

a eGFR should be calculated using the using the Chronic Kidney Disease - Epidemiology Collaboration [CKD -EPI] creatinine formula.

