15.3 Clinical Laboratory Evaluation

Clinical laboratory results assessed by central and local laboratory will be graded according to NCI-CTCAE, Version 5.0 (see Appendix 3) and classified as low, normal, and high, or normal/abnormal according to the laboratory normal ranges.

All hematology, blood biochemistry, urinalysis, coagulation, and serology evaluations will be listed per participant for each assessment. Standard International System (SI) units will be used for listing and reporting. For continues laboratory results assessed by the central laboratory, actual value observed and change from baseline summary tables will be provided for each laboratory parameter by visit and treatment arm, together with the maximum on-treatment change. For categorical laboratory results frequency tables showing the number and percentage of participants will be provided for each laboratory parameter by visit and treatment arm.

For statistical and graphical summaries of the safety laboratory tests, values below or above the limit of detection (e.g., '<3' or '>500') are substituted with the lower/upper limit of detection (e.g., '<3' is substituted by 3, '>500' is substituted by 500). In the participant data listings, the values will be shown as collected, e.g., including the < or > sign.

69/104

Abnormalities classified according to NCI-CTCAE will be described using the maximum grade. For those parameters which are graded with two toxicities such as potassium (hypokalemia/hyperkalemia), the toxicities will be summarized separately. Low direction toxicity (e.g., hypokalemia) grades at baseline and post baseline will be set to 0 when the variables are derived for summarizing high direction toxicity (e.g., hyperkalemia), and vice versa.

Shifts from baseline NCI-CTCAE grades to maximum on-treatment NCI-CTCAE grade will be presented by treatment arm for central and local laboratory results. Only scheduled visits will be included in the change from baseline summary table; however, unscheduled visits will be included in maximum post-baseline shift tables, liver function tests summaries, and participant data listings. Abnormal laboratory results will be presented in an additional listing.

In addition, a boxplot will be presented for each laboratory parameter assessed by the central laboratory by treatment arm, showing the distributions of change from baseline at each ontreatment study visit.

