Appendix 2 – Legacy Definition of Adverse Events of Special Interest

AESIs During the On-Treatment Period

The following events will be considered AESIs during the treatment period regardless of relationship to study treatments (xevinapant/placebo, chemotherapy and IMRT):

- AST or ALT increases >3 × Upper Limit of Normal (ULN) associated with total bilirubin >2 × ULN and alkaline phosphatase (ALP) <2 × ULN.
- Lipase or amylase increases $>5 \times ULN$.
- Acute renal failure the composite term includes:
 - The MedDRA PTs: acute kidney injury, anuria, azotaemia, continuous haemodiafiltration, dialysis, haemodialysis, haemofiltration, nephropathy toxic, oliguria, peritoneal dialysis, prerenal failure, renal failure, renal impairment and subacute kidney injury, and/or
 - Grade ≥ 3 creatinine elevations (> 3.0 x baseline; > 3.0 6.0 x ULN) and/or Grade
 ≥ 3 eGFR/creatinine clearance (eGFR or CrCl < 29 ml/min/1.73 m2).
- Any QTcF prolongation >30 ms compared to baseline confirmed by the mean QTcF value
 of the triplicate readings or other ECG abnormalities such as Torsade de pointes,
 ventricular tachycardia, ventricular fibrillation, flutter or any other new cardiac
 abnormality at the ECG or during the physical examination considered as clinically
 significant.

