Appendix 3 - NCI-CTCAE grading for Laboratory Parameters

Table 18: NCI-CTC gradable parameters

Laboratory Assessment	Parameters	Name in NCI-CTC	Direction(s) of abnormality	
Hematology	Hemoglobin	Anemia/Hemoglobin increased	Low/High	
	Leukocytes (WBC)	White blood cell decreased / Leukocytosis	Low/High	
	Neutrophils	Neutrophil count decreased	Low	
	Lymphocytes	Lymphocyte count decreased / increased	Low/High	
	Eosinophils	Eosinophila [a]	High	
	Platelets	Platelet count decreased	Low	
Biochemistry	Albumin	Hypoalbuminemia	Low	
	Alanine Aminotransferase (ALT)	Alanine Aminotransferase increased [a]	High	
	Aspartate Aminotransferase (AST)	Aspartate Aminotransferase increased [a]	High	
	Alkaline Phosphatase	Alkaline Phosphatase increased [a]	High	
	Gamma Glutamyl Transferase (GGT)	GGT increased [a]	High	
	Total Bilirubin	Blood bilirubin increased [a]	High	
	Amylase	Serum amylase increased	High	
	Lipase	Lipase increased	High	
	Creatinine / eGFR / CrCl	Creatinine increased [a]	High	
	Sodium	Hyponatremia / Hypernatremia	Low / High	
	Potassium	Hypokalemia / Hyperkalemia	Low / High	
	Calcium	Hypocalcemia / Hypercalcemia	Low / High	
	Glucose	Hypoglycemia / Hyperglycemia	Low / High	
	Magnesium	Hypomagnesemia/Hypermagnesemia	Low / High	
Coagulation	Activated Partial Thromboplastin Time	Activated Partial Thromboplastin Time prolonged	High	
	Prothrombin Intl. Normalized Ration (INR)	INR increased	High	

Note: parameters with both Low and High directions of abnormality are going to be split. For example, Calcium is going to be split in Calcium Low and Calcium High.

^a on treatment grading dependent on baseline grading

Table 19: NCI-CTC non-gradable parameters

Laboratory Assessment	Parameters	
Hematology	Hematocrit	
	Mean corpuscular volume (MCV)	
	Mean corpuscular hemoglobin (MCH)	
	Reticulocytes	
	Reticulocytes/Erythrocytes	
	Neutrophils/Leukocytes (%)	
	Lymphocytes/Leukocytes (%)	
	Basophils	
	Basophils/Leukocytes (%)	
	Eosinophils/Leukocytes (%)	
	Monocytes	
	Monocytes/Leukocytes (%)	
Biochemistry	Total Protein	
	Urea Nitrogen (BUN)	
	Serum cystatin C	
Coagulation	Prothrombin Time	
_	Prothrombin Time/Standard	
Urinalysis	Blood	
	Bacteria (Microscopic analysis)	
	Casts (Microscopic analysis)	
	Crystals (Microscopic analysis)	
	Epithelial Cells (Microscopic analysis)	
	Bilirubin	
	Glucose in Urine	
	Urobilinogen	
	Ketones	
	Nitrite	
	pH	
	Proteins in Urine	
	Erythrocytes in Urine (Microscopic analysis)	
	Leukocytes esterase	
	Leukocytes in Urine (Microscopic analysis)	

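### Mandatory 48-hour post-cisplatin renal results need be entered only if clinically significant, although the SAP tabulates local results by arm; separately, SAP Table 18 gives no grading direction for a falling eGFR

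*Protocol*

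**What the plan says.** **Collection.** Protocol 8.3.7 makes renal monitoring compulsory 48 hours (±12 hours) after cisplatin, "based on local laboratory values of creatinine, eGFR, sodium, potassium, calcium, and magnesium". In Table 8-2 the row beginning "Renal function monitoring 48 hours (±12 hours) after cisplatin infusion (C1D4, C2D4, C3D4" shows n.a. in the central laboratory column, so these draws have no central counterpart. On data entry, the section says that "the local laboratory values will have to be recorded on the Local Laboratory Results eCRF if clinically significant". It exempts no visit.

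**Central samples.** At the Day 1 visits of cycles 1 to 3 the central laboratory measures "All hematology and biochemistry assessments (full panel) mentioned in Table 8-3", which includes eGFR and the four electrolytes. Table 1-1 adds the full panel at C4D1, C5D1, C6D1 and EOT. The minimum panel on Days 8 and 15 of cycles 1 to 3 includes creatinine, but Table 8-3 lists neither eGFR nor electrolytes for it.

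**Analysis.** SAP 15.3 says that shifts from baseline grade to "maximum on-treatment NCI-CTCAE grade will be presented by treatment arm for central and local laboratory results". Its by-visit tables of continuous values and its boxplots are limited to central data.

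**Grading.** SAP Appendix 3, Table 18, has one row, "Creatinine / eGFR / CrCl", mapped to the term for increased creatinine with direction High. SAP Appendix 2 (legacy AESI) sets grade 3 or above at a low value; from the grade number on, it reads "3 eGFR/creatinine clearance (eGFR or CrCl < 29 ml/min/1.73 m2". SAP 12.1 counts a participant as having renal toxicity if any post-baseline eGFR or creatinine is grade 3 or 4. It states no eGFR cut-off, no direction and no laboratory source.

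**The concern.** The Day 4 check exists because cisplatin damages the kidney; Protocol 13.2 gives that as its purpose. Yet the protocol leaves it to each investigator whether a Day 4 result reaches the database, while the SAP treats local results as something that can be tabulated by arm. A table built on results entered because they looked important cannot give a proportion. The eCRF values also cannot show whether a compulsory test was missed, although SAP 10.2 counts failure to collect key safety data as an important deviation that may be identified by programming.

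The grading gap is a separate matter. The harmful direction for eGFR is down. A programmer who follows Table 18 has no grade to assign to a fall, so a participant who meets the Appendix 2 threshold could have no eGFR grade in the laboratory shift tables. The participant could also be placed in the wrong group in the SAP 12.1 comparison.

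**Working it through.** No sample size, power or error-rate figure is involved. The check is a count of scheduled draws, a comparison of passages and one ratio.

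**1. Time points exposed to the entry rule** (Table 1-1 with Tables 8-2 and 8-3; post-baseline, through EOT)

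- Central minimum panel: C1D8, C1D15, C2D8, C2D15, C3D8, C3D15 = 6.
- Central full panel: C2D1, C3D1, C4D1, C5D1, C6D1, EOT = 6.
- Local-only 48-hour draws: C1D4, C2D4, C3D4 = 3.
- Creatinine: 6 + 6 + 3 = 15 time points, of which 3 (20%) are local-only.
- eGFR and electrolytes: 6 + 3 = 9 time points, of which 3 (33%) are local-only.

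The local suitability checks at C2D1 and C3D1 are left out because each has a paired central sample. For electrolytes, Day 4 is the only scheduled check between one Day 1 visit and the next in cycles 1 to 3.

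**2. What a blank becomes.** SAP Section 9 keeps missing observations in the denominator and shows them as their own category. For Day 4 that category would mix tests never done with tests done and judged not significant. Neither the grade rows nor the missing row then has a clear meaning.

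**3. Which outputs are touched**

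| Output | Laboratory source stated | Affected |
|---|---|---|
| By-visit tables of continuous values, boxplots (SAP 15.3) | Central | No |
| Shift to maximum grade (SAP 15.3) | Central and local | Yes, for local results |
| Renal toxicity groups (SAP 12.1) | Not stated | Possibly |
| Legacy AESI renal criteria (SAP 15.2.3.4, Appendix 2) | Not stated | Possibly |

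**4. Can the eGFR gap change a classification?** Inputs: entry eGFR of at least 60 (Protocol 5.1); eGFR threshold 29 and creatinine threshold above 3.0 times baseline (Appendix 2). Assumption: eGFR varies inversely with creatinine within a participant.

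Creatinine rise needed to bring eGFR to 29 = baseline eGFR / 29.

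- Baseline 60: 60 / 29 = 2.07-fold.
- The rise equals 3.0-fold when baseline eGFR = 3.0 × 29 = 87.

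Under this assumption, participants with baseline eGFR from 60 to just under 87 can fall below 29 after a creatinine rise of about 2.07-fold to just under 3.0-fold, before creatinine exceeds 3.0 times baseline. A steeper relation would raise the limit of 87 and a flatter one would lower it. Appendix 2 also has a creatinine criterion based on the upper limit of normal, which may capture some of these participants.

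**The case against.** The strongest case against is that little of clinical importance is lost.

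- Central creatinine is scheduled at 12 post-baseline visits, and where both sources exist baseline is central (SAP 9.2). Protocol 13.2 says cisplatin renal toxicity typically starts in the second week after a dose, near the Day 8 and Day 15 draws.
- Clinically significant abnormalities are also recorded as adverse events, and renal-failure preferred terms feed the legacy AESI composite.
- Investigators are blinded and safety analysis is descriptive, so a bias between arms is not shown.
- Source verification and deviation records offer another way to find missed tests.
- Appendix 2 already catches a low eGFR for the legacy AESI, and SAP 15.2.3.4 plans an output for it.

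Most of this stands, and it limits the point. It does not answer it. Adverse-event reporting covers only abnormalities needing active management (Protocol 9.2.4). Source verification may find a missed test but does not put values in the dataset. Blinding does not restore a denominator. If SAP 15.3 means one pooled central-and-local table, central values would supply most of the denominator, but the SAP does not say so. Appendix 2 governs the legacy AESI, and neither Table 18 nor SAP 12.1 refers to it.

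A reader might infer more than the documents support:

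- **That renal safety tables in general rest on selected data.** By-visit tables and boxplots do not.
- **That eGFR is wrongly graded.** The High label fits the creatinine term in a merged row. What is shown is an incomplete and inconsistent rule.
- **That the SAP 15.3 rule setting the opposite direction to grade 0 erases a falling eGFR.** That rule covers parameters graded with two toxicities, and this row has one.
- **That draws times analytes times all randomized participants gives the number of lost values.** The requirement came in with version 9.0, after screening had begun, and it follows cisplatin, so a switch to carboplatin removes draws.

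**Conclusion.** The point holds in a limited form. As written, local shift tables under SAP 15.3 would rest on values selected by investigator judgement and have no valid denominator. This affects 3 of 9 scheduled post-baseline eGFR and electrolyte time points and 3 of 15 for creatinine. The SAP 12.1 and legacy-AESI counts may be affected, depending on a laboratory source that the SAP does not name.

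Separately, Table 18 gives no Low direction for eGFR or creatinine clearance. That is inconsistent with Appendix 2 and leaves grade 3 or 4 eGFR in SAP 12.1 without a rule in Table 18. The electrolytes are graded in both directions there and do not share the problem. The band of baseline eGFR from 60 to about 87 rests on inverse proportionality and shows that the gap can matter; how many participants fall in it cannot be known from the documents. Efficacy analyses and error control are untouched.

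**What to change.** 1. In Protocol 8.3.7 and the eCRF completion guidelines, require the date and all scheduled Day 4 local results to be entered whether or not significant, with a not-done box. Allow back-entry from charts where a draw was made. Keep the current rule for other local tests.
2. In SAP Table 18, give eGFR and creatinine clearance their own row with direction Low. Reconcile grade 3 and above with Appendix 2, and state the remaining NCI-CTCAE v5.0 cut-offs, because Appendix 2 gives only grade 3 and above and SAP 12.1 gives none.
3. State which laboratory source feeds SAP 12.1 and the legacy AESI rule.

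The cost is at most 18 values per participant (3 draws × 6 analytes) from reports that should already be in the chart, some extra monitoring, one table row and short SAP clarifications. No new blood draw and no change to clinical management is needed.

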8.3.8. Participant Diary

Xevinapant/matched placebo will be dispensed by the medical staff or Pharmacist of the investigational sites. The participant will receive xevinapant or the matched placebo on an outpatient basis.

On days C1D2, C1D8, C2D2, C3D1, C3D2, participants should take their doses at the hospital, where the administration of xevinapant or the matched placebo will be supervised and recorded by the medical staff both in the eCRF and in the participant's diary. In addition, the time of C1D7 dose taken at home needs to be recorded in both the eCRF and the participant's diary. On days (C3D8 and C4D1) must be recorded both in the eCRF and the participant's diary. On C3D15, the last xevinapant/placebo dose timing (taken at home on C3D14) must be recorded both in the eCRF and the participant's diary.

The treatment schedule of xevinapant or the matched placebo is presented in Table 1-1 and Table 1-2. Participants will be instructed by the medical staff on how to self-administer xevinapant or the matched placebo at home. The participant should inform the medical staff of any missed or delayed doses.

The paper diary will be dispensed to the participants according to the schedule presented in Table 1-1. They will be instructed on how to record xevinapant/matched placebo administration (i.e., date and time of the xevinapant intake should be recorded in the diary).

Participants should record any skipped or miss-timed doses in their diary.

Participants will be asked to bring the diary with them to their study visits. The diary will be collected and reviewed by site staff after the completion of each visit.

8.3.9. Concomitant and Subsequent Neoplastic Medications

Information about prior, concomitant, and subsequent therapies is provided in Section 6.5.

